# Table 4.5.1.1-1Investigational Product Dose Preparation; Prefilled
Infusion Bag

Treatment Group (Dose Level)	Number of Vials Required	Capacity of Infusion Bag (mL)	Investigational Product Dose Volume (mL)	Total Filled Bag Volume (mL)	Minimum Dose Administration Time (minutes)
MEDI3902 or placebo	8	Re d	•		
Redact MEDI3902 or placebo	15	Re d			
a The contents of 8 vials equates to Red , therefore following dose preparation find will remain unused in					

The contents of 8 vials equates to real, therefore following dose preparation real will remain unused in one of the vials t

Table 4.5.1.1-2	Investigational Product Dose Preparation; Empty Infusion
	Bag

Treatment Group (Dose Level)	Number of Vials Required	Capacity of Infusion Bag (mL)	Investigational Product Dose Volume(mL)	0.9% (w/v) Saline Volume (mL)	Total Filled Bag Volume (mL)	Minimum Dose Administration Time (minutes)
Redact MEDI3902 or placebo	8	Redacted	I			
Redact MEDI3902 or placebo	15	Re d				

a The contents of 8 vials equates to represent the reformed for the vials to the vials to the vials the reformation of the vials the via

## 4.5.1.2 Treatment Administration

The day of dosing with investigational product is considered Day 1. All subjects must receive the entire dot -mL volume (or dot ml if a decision is made to adjust the dose from dot mg mg MEDI3902) of investigational product (MEDI3902 or placebo) IV unless the infusion is discontinued due to an AE. MEDI3902 or placebo must be infused through a low protein binding up m or dot up m filter using an IV infusion pump over a minimum duration time as mentioned in Table 4.5.1.1-1 and Table 4.5.1.1-2. If the duration of the infusion exceeds 8 hours for the dot mg MEDI3902/placebo groups or 12 hours (in case of dose adjustment) for the dot mg MEDI3902/placebo groups, the medical monitor must be notified immediately. MEDI3902 or placebo must never be administered via IV push or bolus.

During preparation of the investigational product infusion, the capacity of the tubing should be calculated in order to adjust the volume of investigational product solution needed to prime the IV tubing (see example below). This step is necessary because the same volume of saline will be needed at completion of the infusion to flush the IV tubing in order to deliver the complete volume of investigational product solution. Because the IV tubing contains investigational product solution, the flush must be infused using the same infusion rate as that used for the investigational product solution in the infusion bag.

Example:

If the IV tubing capacity is mL, the IV tubing should be primed with mL of investigational product solution from the investigational product infusion bag before initiating the investigational product infusion. Once the investigational product infusion bag

is empty, the IV tubing should be flushed with at least  $\sum_{eq}$  mL of  $\sum_{eq}^{Re}$ % normal saline via infusion pump at the same rate as dosing.

The start time of the investigational product infusion will be the time the infusion of the investigational product solution from the infusion bag (with IV tubing already primed with investigational product solution) is started. The stop time of the infusion should be the time the IV tubing has been flushed to administer the residual investigational product solution.

## 4.5.1.3 Monitoring of Dose Administration

Subjects will be monitored with assessment of vital signs (temperature, respiration rate, heart rate, and blood pressure). Vital signs will be obtained on the day of dosing prior to the start of infusion (2 recordings of blood pressure and pulse rate, 5 minutes apart), every  $30 (\pm 5)$  minutes during investigational product infusion, at completion of infusion ( $\pm 5$  minutes), every  $30 (\pm 5)$  minutes after completion of infusion for 2 hours, and 24 hours ( $\pm 30$  minutes) after completion of infusion.

[figure not shown]
As with any antibody, allergic reactions to dose administration are possible. Therefore, appropriate drugs and medical equipment to treat acute anaphylactic reactions must be immediately available, and study personnel must be trained to recognise and treat anaphylaxis.

## 4.5.1.4 Reporting Product Complaints

Any defects with the investigational product must be reported *immediately* to the MedImmune Product Complaint Department by the site with further notification to the site monitor. All defects will be communicated to MedImmune and investigated further with the Product Complaint Department. During the investigation of the product complaint, all investigational products must be stored at labeled conditions unless otherwise instructed.

MedImmune contact information for reporting product complaints:

## 4.5.2 Additional Study Medications

No other study medications are specified for use in this clinical protocol.

## 4.5.3 Labeling

Labels for the investigational product will be prepared in accordance with Good Manufacturing Practice (GMP) and local regulatory guidelines. The infusion bags will be labeled by an unblinded investigational product manager at the time of use according to site standard operating procedures and instructions provided by MedImmune. The labels will fulfill GMP Annex 13 requirements for labeling. Label text will be translated into local languages, as required.

## 4.5.4 Storage

Store investigational product at 2°C to 8°C.

## 4.5.5 Treatment Compliance

Investigational product is administered by study site personnel, who will monitor compliance.

## 4.5.6 Accountability

The investigator's or site's designated investigational product manager is required to maintain accurate investigational product accountability records. Upon completion of the study, copies of investigational product accountability records will be returned to Sponsor. All unused investigational product will be returned to a Sponsor-authorised depot or disposed of upon authorisation by Sponsor.

## 4.6.2 Methods for Ensuring Blinding

This is a double-blind study in which MEDI3902 and placebo are visually indistinguishable. Neither the subject/legal representative nor any of the investigator or sponsor staff who are involved in the treatment or clinical evaluation of the subjects will be aware of the treatment received (International Council for Harmonisation [ICH] E9). Investigational product will be handled by an unblinded investigational product manager at the site. The unblinded personnel will not reveal the treatment allocation to the sponsor or blinded site staff. In the event that the treatment allocation for a subject becomes known to the investigator or other study staff involved in the management of study subjects, the sponsor must be notified *immediately*. If the treatment allocation for a subject need to be known to treat an individual subject for an AE, the investigator must notify the sponsor *immediately*. The site will maintain a written plan detailing which staff members are blinded/unblinded and the process of investigational product administration used to maintain the blind.

## 4.6.3 Methods for Unblinding

#### 4.6.3.1 Unblinding in the Event of a Medical Emergency

In the event of a medical emergency, the investigator may unblind an individual subject's investigational product allocation. The investigator is encouraged to attempt to contact the medical monitor, prior to unblinding the investigational product allocation for an individual subject, to discuss the medical emergency and the reason for wanting to unblind, as long as it does not jeopardise the safety of the individual subject. Instructions for unblinding an individual subject's investigational product allocation are contained in the IWRS manual. In general, unblinding should only occur if management of the medical emergency would be different based on the subject having received investigational product. In the majority of cases, the management of a medical emergency would be the same whether or not investigational product was received by the subject. If this was the case, the investigational product allocation should not be unblinded.

MedImmune retains the right to unblind the treatment allocation for SAEs that are unexpected and are suspected to be causally related to an investigational product and that potentially require expedited reporting to regulatory authorities.

#### 4.6.3.2 Unblinding for Interim Pharmacokinetic Analysis Purposes

One interim PK analysis is planned. Description of this analysis is provided in Section 4.8.11. To ensure the blinding of each subject's treatment assignment throughout the study, the interim analysis will be performed by a limited number of sponsor personnel who are not involved in the conduct of the study. The PK analysis will be performed by a MedImmune pharmacokineticist, who will present the PK interim analysis data to the DMC. The DMC will be responsible for recommending dose adjustment as outlined in Section 4.8.11. Site investigators and site monitors will remain blinded to the treatment assignment of individual subjects until the last subject completes the study and the database is locked. Sponsor personnel who will have access to the treatment assignments of individual subjects in order to prepare the PK dataset for the analysis will be identified in the unblinding plan. Further details will be included in the unblinding plan before the interim analysis is performed.

# 4.7 Restrictions During the Study and Concomitant Treatment

## 4.7.1 Contraception

Female subjects of child bearing potential (who are sexually active with a nonsterilised male partner) will be advised to avoid becoming pregnant by initiating and continuing at least

1 highly effective method of contraception for 49 days postdose; cessation of contraception after this point should be discussed with a qualified health care provider or a physician. A highly effective method of contraception is defined as one that results in a low failure rate (ie, less than 1% per year) when used consistently and correctly. Periodic abstinence, the rhythm method, and the withdrawal method are not acceptable methods of contraception. The acceptable methods of contraception are described in Table 4.7.1-1.

Nonhormonal Methods	Hormonal Methods
Vasectomised sexual partner	Levonorgestrel-releasing intrauterine system
Tubal occlusion	Medroxyprogesterone injections
IUD	Etonogestrel implants
	• Normal and low-dose combined oral pills
	Norelgestromin/EE transdermal system
	• Intravaginal device (eg, EE and etonogestrel)
	• Desogestrel

## Table 4.7.1-1Highly Effective Methods of Contraception

EE = ethnyl estradiol; IUD = intrauterine device

## 4.7.2 Concomitant Medication

The Investigator must be informed as soon as possible about any medication taken from the time of screening until the end of the clinical phase of the study (final study visit). Any concomitant medication(s), including herbal preparations, taken during the study will be recorded in the electronic case report forms (eCRFs).

## 4.7.2.1 Permitted Concomitant Medications

All subjects will be premedicated with antihistamine, for example, be mg diphenhydramine IV, clemastine mg IV, or dexchlorpheniramine mg IV (or another antihistamine preparation utilised in routine clinical practice for management of acute allergic reactions). Additional suggested concomitant medications in the event of an infusion reaction are summarised in Section 3.1.3.

Investigators may prescribe concomitant medications or treatments deemed necessary to provide adequate therapeutic and supportive care. Specifically, subjects should receive full medical care during the study, including contraceptives, transfusions of blood and blood products, and treatment with antibiotics, anti-emetics, anti-diarrheals, analgesics, and other care as deemed appropriate, and in accordance with their institutional guidelines.

#### 4.7.2.2 Prohibited Concomitant Medications

Investigators are reminded to minimise concomitant medication use unless necessary for medical management. Any other experimental/investigational products are prohibited through 49 days postdose. The sponsor must be notified in the event that a subject was to receive an investigational product during the study.

## **Analysis Populations**

The ITT Population is defined as all subjects who are randomised. Subjects will be analysed by the treatment group corresponding to their randomised treatment.

The mITT Population is defined as all subjects who are randomised into the study and who receive any amount of investigational product. Subjects will be analysed by the treatment group corresponding to their randomised treatment. All analyses, with the exception of safety, will be performed on the mITT Population.

The As-treated Population will include all subjects who are randomised into the study and who receive any amount of investigational product. Subjects will be analysed by the

treatment group corresponding to the treatment actually received. All safety analyses will be performed on the As-treated Population.

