3.2 Analysis Populations

The analysis populations are defined in Table 1.

Table 1 Analysis Populations

Population	Description
ITT	All subjects who are randomized. Subjects will be analyzed according to their randomized treatment group.
modified ITT (mITT) population	Subjects who receive any study investigational product will be included in the mITT population and subjects will be analyzed according to their randomized treatment group.
As-Treated population	Subjects who receive any study investigational product will be included in the As Treated population and subjects will be analyzed according to the treatment they actually receive.

ITT = intent-to-treat

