3.4.3 Study Drug Exposure

The amount of investigational product infused will be summarized by milligrams (mg) for subjects in the 'As-Treated' population by treatment group. The actual total amount of investigational product infused will be calculated based on the treatment group to which the subject was assigned and the dose intensity. If the entire dose was administered, the dose intensity will be assumed to be 100%. If the entire dose was not administered, dose intensity will be calculated as a percentage of actual volume of investigational product given (mL) against the volume that was intended to be administered (ie, 100 mL). The actual total amount of investigational product infused (mg) = dose intensity * treatment group (mg). For this study, the IV treatment group is either **Redacted** mg, or **Redacted** mg or **Redacted** mg **Redacted** **Redacted**

An additional table will summarise the number of infusion interruptions and the median length of interruptions (minutes).

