3.9 Antidrug antibody Response

The number and percentage of subjects who develop anti-MEDI3902 antibodies will be summarized at each visit by treatment group and for MEDI3902 total. Subjects will be excluded from the summary of an individual visit if data to that specific visit are missing. For those with a positive assessment or borderline positive assessment, the ADA titer results will also be summarized. Antidrug antibody values reported as borderline positive (ie, \leq LLOQ), a value equal to LLOQ will be imputed in the summaries. An additional table will summarise the number and percentage of subjects positive for ADA at baseline (ie, ADA prevalence) and positive at any post-baseline time point (ie, ADA incidence). For those with a positive post-

baseline assessment, the percentage who were persistent positive and transient positive will also be presented.

5. Persistent positive is defined as positive at ≥ 2 post-baseline assessments (with ≥ 16 weeks between first and last positive) or positive at last post-baseline assessment.
6. Transient positive is defined as negative at last post-baseline assessment and positive at only one post-baseline assessment or at ≥ 2 post-baseline assessments (with < 16 weeks between first and last positive).

AEs will be summarized by SOC and PT based on MedDRA for subjects with ADA to MEDI3902 at any time post-baseline. The impact of ADA on PK will be included in the PK report as mentioned in Section 3.10.

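### ADA (and PK, unless a separate document says otherwise) is summarised by randomised rather than received treatment, and the SAP's As-Treated exposure table takes its milligrams from the assigned group

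*Protocol*

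**What the plan says.** **Analysis sets.** Protocol 4.8.1 (Analysis Populations) states "All analyses, with the exception of safety, will be performed on the mITT Population" and, for that set, "Subjects will be analysed by the treatment group corresponding to their randomised treatment". SAP 3.2 agrees: dosed subjects "will be included in the mITT population and subjects will be analyzed according to their randomized treatment group". The only set grouped by treatment received is the As-treated Population, which the protocol reserves for safety: "All safety analyses will be performed on the As-treated Population".

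**ADA and PK.** Both are secondary endpoints (protocol 2.2.2) with sections separate from safety: protocol 4.8.6 and 4.8.7, SAP 3.9 and 3.10. None of these sections names a population. SAP 3.9 says only: "The number and percentage of subjects who develop anti-MEDI3902 antibodies will be summarized at each visit by treatment group". SAP 3.10 leaves the detail of the PK analyses to a separate PK Report. SAP section 4 leaves the detail of the PK interim to an Interim Analysis Plan.

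**Exposure.** SAP 3.4.3 places the table of milligrams infused in the As-Treated population. Yet each subject's amount is "calculated based on the treatment group to which the subject was assigned and the dose intensity". For an incomplete infusion, dose intensity is the volume given "against the volume that was intended to be administered (ie, 100 mL"). Protocol 4.5.1.2 states one volume, blacked out, and then a second, also blacked out: "ml if a decision is made to adjust the dose".

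**The concern.** Concentrations, anti-drug antibodies and milligrams infused describe the product that entered the patient. Grouping by randomised treatment protects a comparison of outcomes between arms. It gives no such protection to these summaries, and after a wrong-product or wrong-dose error it attaches the data to a treatment that was not given.

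Three things are at stake:

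- **ADA.** A MEDI3902 recipient randomised to placebo would contribute any treatment-induced antibody to the placebo column, where it could pass for assay background. Adverse events are summarised by treatment received, so the same subject could sit in one column for ADA and in another for the linked adverse events.
- **PK.** The Day 22 mean at the interim informs a possible dose adjustment and may rest on as few as 10 subjects per group.
- **Exposure.** The table can show a MEDI3902 recipient with no MEDI3902, or a placebo recipient with a full dose of it.

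**Working it through.** The plan gives no figure on this point to reproduce. The check is mainly a reading of the rules, with one illustration of size.

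**1. Which grouping applies to which summary**

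| Summary | Set named in its own section | Grouping that results |
|---|---|---|
| Adverse events, laboratory | As-treated (protocol 4.8.4, SAP 3.8) | Received |
| ADA | None (protocol 4.8.7, SAP 3.9) | Randomised, by the general rule in protocol 4.8.1 |
| PK | None (protocol 4.8.6, SAP 3.10); detail deferred | Randomised, unless the PK Report or Interim Analysis Plan says otherwise |
| Milligrams infused | As-Treated (SAP 3.4.3) | Column: received. Value: assigned |

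The mITT and As-treated sets contain the same people, namely all randomised subjects who received any product. Only the group label can differ, and only for a subject given the wrong product or the wrong dose level.

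**2. Size for PK, as an illustration**

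Assume that k of n active-randomised subjects received placebo and have zero concentration, and that the rest have mean m. Grouped as received, the active mean is m. Grouped as randomised, it is m × (n − k)/n, so the ratio is 1 − k/n.

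- n = 10 (the interim minimum, protocol 4.8.11): 0.90, 0.80 and 0.70 for k = 1, 2 and 3.
- n = 143 (planned group size): 0.993, 0.986 and 0.979.
- With the planned 20% attrition, 143 × 0.8 = 114.4. With n = 114 and k = 1, the ratio is 1 − 1/114 = 0.991.

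The values of k are assumptions. A wrong-dose-level error cannot be sized, because the dose levels are largely blacked out.

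**3. Size for ADA**

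One relabelled subject changes an ADA count by at most one. Among 143 subjects that is about 1/143 = 0.7 percentage points.

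**4. The exposure formula**

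SAP 3.4.3 sets milligrams = dose intensity × group dose, with the group taken as assigned. Let D be the MEDI3902 group dose, and take placebo as 0 mg (an assumption, since the doses listed there are redacted). With full infusion:

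- Assigned placebo, received MEDI3902: MEDI3902 column, 100% × 0 = 0 mg.
- Assigned MEDI3902, received placebo: placebo column, 100% × D = D mg.
- Correct product, partly infused: correct column, with D scaled by dose intensity. There is no grouping problem.

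**5. The fixed volume**

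If v mL were given and V mL intended, dose intensity should be v/V. The SAP's bracketed figure gives v/100. The two agree only when V = 100, and one constant cannot fit two different intended volumes. Under SAP 3.4.3 a complete infusion is set to 100% without using the volume, so only incomplete infusions are affected. Both volumes in protocol 4.5.1.2 and the volume entries in Tables 4.5.1.1-1 and 4.5.1.1-2 are redacted, so no size can be given.

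**The case against.** **The general sentence is not applied literally.** The SAP summarises demographics in ITT as well as mITT, and exposure in As-Treated. It could be said that the ADA and PK sets are simply unstated. That is fair as far as it goes. But the SAP names those exceptions explicitly and names none for ADA or PK, so the protocol's rule is the only one left. Nor can ADA be treated as safety by default: it is a secondary endpoint and stands outside the safety sections of both documents.

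**PK detail sits elsewhere.** The SAP's version history says the PK population was removed because PK would be reported separately. The PK Report or the Interim Analysis Plan may already group by treatment received. This stands, and the PK part is conditional on it. A reader might infer that the interim mean would be 10% too low and mislead the dose decision. The documents do not support that. They show no wrong-product error, the interim rules are not visible, and a mean below target leads only to an adjustment being considered.

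**Errors may be rare and noticed.** Cartons are open-labelled, the product manager is unblinded, the IWRS assigns vial numbers, and only MEDI3902 needs reconstitution. This lowers the likely impact. The plan nevertheless defines an As-treated set, which serves no purpose unless such errors can happen.

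**The word for assignment in SAP 3.4.3 may be loose drafting.** That is plausible, but a programmer following the text would use the assigned dose.

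**The 100 mL is a gloss on the intended volume and matters only if the dose is adjusted.** This also stands in part. SAP 3.1 names no adjusted dose for the key analyses, yet SAP 2.2, 2.4 and section 4 keep the adjustment open.

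**Conclusion.** The point holds as a minor defect of stated rules. ADA is the firmest part, because SAP 3.9 specifies it fully and defers nothing. PK follows the same rule unless an unseen document overrides it. The milligram calculation in SAP 3.4.3 contradicts the population in which it is tabulated.

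Two stronger readings should be resisted. One is that any dosing error misplaces data. It does not: a partial or interrupted infusion of the correct product keeps its group and is handled through dose intensity. The other is that exposure is tabulated in the wrong column. It is not: the column follows treatment received, and it is the milligram value that is wrong.

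The size is zero if nobody receives the wrong product or dose level, and the documents give no expected number. The ratios 0.90 (10 subjects) and 0.993 (143 subjects) assume one active-randomised subject with zero concentration and randomised grouping of PK. Primary efficacy and its planned sample size are unaffected.

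**What to change.** - **Protocol 4.8.1, SAP 3.9 and SAP 3.10:** state that ADA and PK summaries use the As-treated Population, grouped by treatment received. Carry the same rule into the PK Report and the Interim Analysis Plan, including the Day 22 interim mean.
- **SAP 3.4.3, milligrams:** compute the amount from the treatment actually received, multiplied by dose intensity.
- **SAP 3.4.3, volume:** reconcile the single 100 mL with the protocol's intended volume for each dose in 4.5.1.2 and the dose preparation tables, so that the denominator follows the dose concerned.

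The cost is wording in one protocol section and three SAP sections, plus alignment of the two separate PK documents. No new data are needed, no subject enters or leaves an analysis set, and the efficacy analysis stays by randomised group.
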